2.5.4 Supportive analyses

As sensitivity analysis, ORR will be calculated and summarized for patients from the Evaluable Set. ORR will be summarized using descriptive statistics (N, %) by treatment arm along with two-sided exact binomial 95% CIs [Clopper CJ and Pearson ES. (1934) The use of confidence or fiducial limits illustrated in the case of the binomial. Biometrical, 26, 404-413]. Further sensitivity analyses identifying possible outcome scenarios may be performed in the event of patients being randomized but not treated.

New anticancer therapy sensitivity analysis for ORR

The analyses of ORR will be repeated using a stricter ITT approach i.e including all response assessments irrespective of new anti-neoplastic therapy using the FAS. This analysis will only be performed if data permits.

Response evaluations recorded after the initiation of new anti-neoplastic therapy will be included in sensitivity analysis of ORR, (i.e. the occurrence of new anti-neoplastic therapy will be ignored for the analyses). The sensitivity analyses will be performed based on both the investigator and independent review assessments using the FAS. In the summary tables, this approach is referred as 'new anticancer therapy ORR sensitivity.

ORR based on radiographic response by independent review assessment

The analyses of ORR will be repeated based on radiographic response assessed by independent review by only incorporating the radiographic data which includes the lesion measurements

from target lesions, non-target lesions, and new lesion per RANO. Clinical status data and corticosteroid use data will not be considered for the supportive analyses based on radiographic response. Waterfall plot will be presented for this analysis.

Waterfall graphs will be used to depict the anti-tumor activity for independent and investigator assessments. These plots will display the best percentage change from baseline in the sum of the products of perpendicular diameters of all target lesions for each patient. Only patients with measurable disease at baseline will be included in the waterfall graphs. Special consideration is needed for assessments where the target lesion response is CR, PR or SD, but the appearance of a new lesion or a worsening of non-target lesions results in an overall lesion response of PD. A patient with only such assessments will be represented by a special symbol (e.g. *) in the waterfall graph. Assessments with "unknown" target lesion response and assessments with unknown overall response will be denoted in the waterfall plots. Patients without any valid assessments will be completely excluded from the graphs.

The total number of patients displayed in the graph will be shown and this number will be used as the denominator for calculating the percentages of patients with tumor shrinkage and tumor growth. Bars will have different fill patterns for all possible values of overall response. Footnote will explain the reason for excluding some patients (due to absence of any valid assessment).

All possible assessment scenarios are described in Table 2-12.

	Criteria for inclusion/exclusion				Possible sources of contradictions	
case	Target response	Overall lesion response	Include in waterfall?	Non-target response	New lesion?	
1	CR/PR/SD	PD	Yes as a bar	PD	any	
2	CR/PR/SD	PD	Yes as a bar	any	Yes	
3	UNK	UNK or PD	Yes as an x	any	any	
4	CR/PR/SD	UNK	Yes as a bar	UNK	No	
5	CR/PR/SD	CR/PR/SD	Yes as a bar	SD/IR	No	
6	PD	PD	Yes as a bar	any	any	

 Table 2-12
 Inclusion/exclusion of assessments used in waterfall graph

Additionally, swimmer plots of time to onset and DOR based on independent and investigator review will be created for the FAS.

Concordance analysis of ORR

An assessment of the concordance between central independent reviewer assessment and local investigator assessment of the BOR for each patient will be provided. The calculation will be based on the percent agreement (the proportion of response outcomes that agree or match across both independent reviewer and investigator assessments).

Reasons for "Unknown" BOR

Patients with 'unknown' BOR will be summarized by reason for having unknown status. The following reasons will be used:

- No valid post-baseline assessment
- All post-baseline assessments have overall lesion response UNK
- New anti-neoplastic therapy started before first post-baseline assessment
- SD and/or unconfirmed CR/PR only occurring prior to week 16 visit

2.6 Analysis of the key secondary objective

Not Applicable.

2.7 Analysis of secondary efficacy objective(s)

The secondary efficacy objectives are to:

- Evaluate ORR of dabrafenib in combination with trametinib versus carboplatin with vincristine, as measured by investigator review per RANO
- Evaluate DOR of dabrafenib in combination with trametinib versus carboplatin with vincristine by both investigator and central independent review per RANO
- Evaluate PFS of dabrafenib in combination with trametinib versus carboplatin with vincristine, as measured by both investigator and central independent review per RANO
- Evaluate TTR of dabrafenib in combination with trametinib versus carboplatin with vincristine, as measured by both investigator and central independent review per RANO
- Evaluate CBR of dabrafenib in combination with trametinib versus carboplatin with vincristine, as measured by both investigator and central independent review per RANO
- Evaluate OS of dabrafenib in combination with trametinib versus carboplatin with vincristine

2.7.1 Secondary endpoints

ORR by investigator review

The evaluation of ORR will be repeated by investigator review assessment as per RANO criteria based on the FAS and the Evaluable Set separately.

Duration of response

DOR only applies to patients whose BOR is CR or PR according to RANO criteria. The start date is the date of first documented response of CR or PR (i.e., the start date of response, not the date when response was confirmed), and the end date is defined as the date of the first documented progression per RANO or death due to any cause. If a patient has not progressed or died or has received any further anticancer therapy at the analysis cut-off date, DOR will be censored at the date of the last adequate tumor evaluation date before the cut-off date or before the start of the new anticancer therapy date, whichever is earlier (see Section 2.7.3).

Novartis
SAP Final CSR LGG

DOR will be analyzed as per investigator and central independent reviewer assessments separately. The analyses of DOR will be based on the FAS and will be repeated based on the Evaluable set.

Progression-free survival

PFS is defined as the time from the date of randomization to the date of the first documented progression or death due to any cause. PFS will be calculated using RANO criteria based on investigators and central independent review of tumor assessments separately. The analysis will include all data observed up-to the cut-off date. If a patient has not progressed or died or has received any further anticancer therapy at the analysis cut-off date, PFS will be censored at the date of the last adequate tumor evaluation date before the cut-off date or before the start of the new anticancer therapy date, whichever is earlier. (See Section 2.7.3 for additional details regarding censoring rules and determination of date of last adequate tumor assessment). Discontinuation due to disease progression (collected on the 'End of treatment' and 'End of post treatment follow up' disposition pages without supporting evidence satisfying progression criteria per RANO will not be considered disease progression for PFS derivation. The analysis will be based on FAS and Evaluable Set separately.

Time to response

TTR is the time from date of randomization to first documented response of CR or PR (which must be confirmed subsequently) according to RANO criteria. All patients in the FAS will be included in the time to response calculation. Patients who did not achieve a confirmed PR or CR will be censored at:

- the maximum follow-up time (i.e. FPFV LPLV used for the analysis) for patients who had a PFS event (i.e. either progressed or died due to any cause);
- the last adequate tumor assessment date for all other patients.

TTR will be analyzed using investigator and independent reviewer assessments separately.

Clinical Benefit Rate

CBR is defined as the proportion of patients with a BOR of CR or PR, or an overall lesion response of SD which lasts for a minimum time duration of 24 weeks. A patient will be considered to have SD for 24 weeks or longer if a SD response is recorded at 23 weeks or later (i.e. ≥ 161 days) from randomization, allowing for the ± 1 week visit window for tumor assessments.

CBR will be analyzed using investigator and independent reviewer assessments separately. CBR will be calculated using the FAS set and Evaluable Set separately.

Overall Survival

OS is defined as the time from date of randomization to date of death due to any cause.

If a patient is not known to have died at the time of analysis cut-off, OS will be censored at the date of last contact (Section 2.1.1).

2.7.2 Statistical hypothesis, model, and method of analysis

ORR by investigator review

The analyses performed at the time of final analysis will only be considered descriptive and therefore no inferential analyses or hypothesis tests will be performed for any secondary objective.

ORR assessed by investigator review per RANO criteria will be summarized by treatment group using descriptive statistics (N, %) by treatment arm along with two-sided exact binomial 95% CIs [Clopper CJ and Pearson ES. (1934) The use of confidence or fiducial limits illustrated in the case of the binomial. Biometrical, 26, 404-413]. The OR and 95% CI will also be presented.

All response data will be listed by investigator and central independent review assessment.

Duration of response

DOR will be listed and summarized by treatment group for all patients in the FAS with confirmed BOR of CR or PR. The distribution of DOR will be estimated using the Kaplan-Meier method and the median DOR will be presented along with 95% CI only if a sufficient number of responses is observed. In addition, Kaplan-Meier estimated probabilities with corresponding 95% CIs [Kalbfleisch JD and Prentice RL. (2002)] at several time points (including at least 4, 6,12 and 18 months) will be summarized.

Progression-Free Survival

The distribution of PFS will be estimated using the Kaplan-Meier method. The results will be plotted graphically by treatment group. The median and 25th and 75th percentiles of PFS along with 95% CI will be presented by treatment group. The hazard ratio for PFS will be calculated, along with its 95% CI, using a Cox model. In addition, Kaplan-Meier estimated probabilities with corresponding 95% CIs at timepoints including 6, 12, 18, and 24 months will be summarized. Censoring reasons will also be summarized.

Time to response

Time to response data will be listed and summarized by treatment group. The distribution of time to response will be estimated using the Kaplan-Meier method and the median time to response will be presented along with 95% CI only if a sufficient number of responses is observed. In addition, a responders-only analysis will also be performed using descriptive summary statistics.

Clinical Benefit Rate

CBR will be summarized by treatment group using descriptive statistics (N, %) by treatment arm along with two-sided exact binomial 95% CIs [Clopper CJ and Pearson ES. (1934) The use of confidence or fiducial limits illustrated in the case of the binomial. Biometrical, 26, 404-413]. The OR and 95% CI will also be presented.

Overall Survival

The survival distribution of OS will be estimated using the Kaplan-Meier method. The results will be plotted graphically by treatment group. The median and 25th and 75th percentiles of OS along with 95% CI will be presented by treatment group. The hazard ratio for OS will be calculated, along with its 95% CI, using a Cox model. In addition, Kaplan-Meier estimated probabilities with corresponding 95% CIs at timepoints up the maximum follow-up (including at least 6, 12, 18, and 24 months will be summarized).

2.7.3 Handling of missing values/censoring/discontinuations

DOR and PFS

If a patient has not progressed or is not known to have died at the date of analysis cut-off or has received any further anticancer therapy, DOR and PFS will be censored at the date of the last adequate tumor before the cut-off date or before the start of the new anticancer therapy date, whichever is earlier.

The date of last adequate tumor assessment is the date of the last tumor assessment with overall lesion response of CR, PR or SD before an event or a censoring reason occurred. In this case the last tumor evaluation date at that assessment will be used. If no post-baseline assessments are available (before an event or a censoring reason occurred) then the date of randomization will be used.

In particular, DOR and PFS will be censored at the last adequate tumor assessment if one of the following occurs: absence of event; the event occurred after a new anticancer therapy is administered; the event occurred after two or more missing tumor assessments. The term "missing adequate tumor assessment" is defined as a tumor assessment (TA) not performed or tumor assessment with overall lesion response of "UNK". The rule to determine number of missing TAs is based on the time interval between the date of last adequate tumor assessment and the date of an event. If the interval is greater than twice the protocol-specified interval between the TAs and 2 times the protocol-allowed time window around assessments, then the number of missing assessments will be 2 or more.

Refer to Table 2-13 for censoring and event date options and outcomes for DOR and PFS.

Situation	Date	Outcome
No baseline assessment	Date of randomization	Censored
Progression or death at or before next scheduled Assessment	Date of progression (or death)	Progressed
Progression or death after exactly one missing assessment	Date of progression (or death)	Progressed
Progression or death after two or more missing assessments	Date of last adequate assessment prior to missed assessment	Censored
No progression (or death) New anticancer therapy (including cancer related surgery and radiotherapy) given prior to protocol defined progression (including patients	Date of last adequate assessment Date of last adequate assessment on or prior to starting new anti- cancer therapy	Censored Censored

Table 2-13Outcome and event/censor dates for DOR and PFS analysis

Novartis	Confidential	Page 38
SAP Final CSR LGG		CDRB436G2201

Situation	Date	Outcome
who crossover from the control arm to the treatment arm)		
Death before first PD assessment	Date of death	Event

Censoring pattern of PFS

Number of patients with a PFS event and number of patients censored for the PFS analysis will be summarized. In addition, a summary of reasons for PFS censoring will be provided by based on the following reasons:

- 1: Ongoing without event
- 2: Lost to follow-up
- 3: Withdrew consent
- 4: Adequate assessment no longer available
- 5: Initiation of new cancer therapy prior to progression
- 6: Event after >=2 missing tumor assessments

The PFS censoring reasons are defined in the following way.

If the time interval between the last adequate TA date and the earliest of the following dates is smaller or equal to interval of 2 missing tumor assessments (see Section 2.7.3 for definition):

- 1. Analysis cut-off date,
- 2. Start date of further anti-neoplastic therapy,
- 3. Date of consent withdrawal,
- 4. Visit date of study treatment discontinuation or end of post-treatment follow-up discontinuation due to lost to follow-up.

Then the PFS censoring reason will be:

- 1. 'Ongoing',
- 2. 'New cancer therapy added',
- 3. 'Withdrew consent',
- 4. 'Lost to follow-up',

If the time interval is larger than the interval of 2 missing tumor assessments with no event observed, then the PFS censoring reason will always default to 'Adequate assessment no longer available'. If the time interval between the last adequate tumor assessment date and the PFS event date is larger than the interval of 2 missing tumor assessments then the patient will be censored and the censoring reason will be 'Event documented after two or more missing tumor assessments'.

These summaries on censoring reasons will be produced for PFS by investigator and central independent reviewers. The censoring patterns will be compared between investigator and central independent reviewers.

Clinical Benefit Rate

Patients with unknown or missing BOR will be counted as non-responders in the analysis of CBR.

OS

If a patient is not known to have died at the time of analysis cut-off, then OS will be censored at the date of last known date patient was alive, i.e., last contact date (see Section 2.1.1).

2.7.4 Supportive analyses

DOR, and PFS based on radiographic response by independent review assessment

The analyses of DOR, and PFS will be repeated based on radiographic response assessed by independent review by only incorporating the radiographic data which includes the lesion measurements from target lesions, non-target lesions, and new lesion per RANO. Clinical status data and corticosteroid use data will not be considered for the supportive analyses based on radiographic response.

New anticancer therapy sensitivity analysis for DOR and PFS

The analyses of DOR and PFS will be repeated using an ITT approach i.e including all response assessments irrespective of new anti-neoplastic therapy using the FAS.

Response evaluations and events (i.e. RANO documented disease progression or death) recorded after the initiation of new anti-neoplastic therapy will be included in sensitivity analyses of DOR and PFS, (i.e. the occurrence of new anti-neoplastic therapy will be ignored for the analyses). The sensitivity analyses will be performed based on both the investigator and independent review assessments using the FAS and using the same statistical methods for DOR and PFS described in Section 2.7.2. In the summary tables, this approach is referred as 'new anticancer therapy DOR sensitivity analysis' and 'new anticancer therapy PFS sensitivity analysis'.

2.8 Safety analyses

All safety analyses will be based on the safety set unless otherwise specified.

2.8.1 Adverse events (AEs)

AEs are coded using MedDRA terminology. The latest available MedDRA version at the time of the analyses should be used. The MedDRA version used for reporting will be specified in the CSR and as a footnote in the applicable tables/listings.

AEs will be assessed according to the Common Terminology Criteria for Adverse Events (CTCAE) version 4.03.

AE summaries will include all AEs occurring during on treatment period. All AEs collected in the AE eCRF page will be listed along with the information collected on those AEs e.g. AE relationship to study drug, AE outcome etc. AEs with start date outside of on-treatment period will be flagged in the listings.

AEs will be summarized by number and percentage of patients having at least one AE, having at least one AE in each primary SOC and for each PT using MedDRA coding. A patient with multiple occurrences of an AE will be counted only once in the respective AE category. A

patient with multiple CTCAE grades for the same PT will be summarized under the maximum CTCAE grade recorded for the event. AE with missing CTCAE grade will be included in the 'All grades' column of the summary tables.

In AE summaries, the primary SOC will be presented alphabetically and the PT will be sorted within primary SOC in descending frequency. The sort order for the preferred term will be based on their frequency in the investigational group (dabrafenib and trametinib).

The following AE summaries will be produced by treatment group: overview of AEs and deaths (number and % of patients with any AE, treatment-related AE, serious adverse events (SAE), fatal AE, AE leading to discontinuation, AE leading to dose reduction/interruption, AEs by SOC and PT, summarized by relationship (all AEs and AEs related to study treatment), seriousness (SAEs and non-SAEs), leading to treatment discontinuation, leading to dose adjustment and/or interruption, leading to dose reduction, and leading to fatal outcome. In addition, a summary of SAEs with number of occurrences will be produced (an occurrence is defined as >1 day between start and prior end date of record of same PT).

For legal requirements of clinicaltrials.gov and EudraCT, two required tables for on-treatment AEs which are not SAEs with an incidence greater than and equal to 5% and on-treatment SAEs and SAEs suspected to be related to study treatment will be provided by SOC and PT on the safety set.

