Patients on dabrafenib and trametinib therapy may continue to receive the assigned study treatment until disease progression by RANO criteria or loss of clinical benefit as determined by the investigator, unacceptable toxicity, start of a new anti-neoplastic therapy, discontinuation at the discretion of the investigator or patient/legal guardian, lost to follow-up, death, or study is terminated by the sponsor. Patients on carboplatin with vincristine chemotherapy will receive one course of induction (10 weeks of treatment with 2 weeks of rest), followed by 8 cycles of

maintenance chemotherapy (6 weeks per cycle consisting of 4 weekly treatments plus 2 weeks of rest). Duration of treatment with carboplatin with vincristine will continue for the prescribed number of cycles as tolerated or unacceptable toxicity, start of a new anti-neoplastic therapy, discontinuation at the discretion of the investigator or patient/legal guardian, lost to follow-up, death, or study is terminated by the sponsor. Patients randomized to the carboplatin with vincristine treatment arm will be allowed to crossover to receive dabrafenib in combination with trametinib treatment after centrally confirmed and RANO-defined disease progression.

Patients receiving dabrafenib with trametinib who have disease progression by RANO criteria may continue study treatment if the investigator determines that patient has clear evidence of clinical benefit from study treatment, continuing study treatment may be in the best interest for the patient, and the patient/legal guardian is willing to continue on study treatment and sign the Informed Consent for treatment beyond progression. The decision to continue study treatment after PD must be documented in the patient records and electronic case report form (eCRF) after every tumor evaluation. In this case, the patient will continue assessments as defined in the study protocol section 7. An End of Treatment visit will be performed when patients permanently discontinue study treatment.

Patients who discontinue dabrafenib with trametinib treatment or complete carboplatin with vincristine treatment without disease progression by RANO criteria will continue tumor assessments as part of the post treatment follow-up outlined in the study protocol section 7 until central independently confirmed disease progression by RANO criteria or death irrespective of start of new anti-neoplastic therapy.

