1.2 Study objectives and endpoints

A list of all study objectives and endpoints is given below. For the final CSR, not all study objectives will be reported, as they have already been analyzed in the primary analysis. This is documented in the corresponding SAP section for each objective.

Objective

Primary

To compare the anti-tumor activity of dabrafenib in combination with trametinib versus carboplatin with vincristine, as measured by overall response rate (ORR) by central independent assessment using the RANO criteria.

[figure not shown]
Secondary

- 1. Evaluate ORR of dabrafenib in combination with trametinib versus carboplatin with vincristine, as measured by investigator review.
- Evaluate the DOR of dabrafenib in combination with trametinib versus carboplatin with vincristine by both investigator and central independent review.
- Evaluate PFS of dabrafenib in combination with trametinib versus carboplatin with vincristine, as measured by both investigator and central independent review.
- Evaluate TTR of dabrafenib in combination with trametinib versus carboplatin with vincristine, as measured by both investigator and central independent review.
- 5. Evaluate CBR of dabrafenib in combination with trametinib versus carboplatin with vincristine, as measured by both investigator and central independent review
- 6. Evaluate the overall survival of dabrafenib in combination with trametinib versus carboplatin with vincristine.
- Evaluate 2-year OS estimates of dabrafenib in combination with trametinib versus carboplatin with vincristine.
- 8. Evaluate the safety and tolerability of dabrafenib in combination with trametinib versus carboplatin with vincristine.
- 9. Evaluate the palatability of dabrafenib and trametinib
- Characterize the pharmacokinetics of dabrafenib, its metabolites and trametinib in the study population
- 11. Assess patient reported outcomes of dabrafenib in combination with trametinib versus carboplatin with vincristine

Endpoint

ORR, proportion of patients with a best overall confirmed Complete Response (CR) or Partial Response (PR) by central independent review per Response Assessment in Neuro-Oncology (RANO) criteria.

- 1. ORR by investigator review assessment per RANO criteria.
- DOR, calculated as the time from the date of the first documented confirmed response (CR or PR) to the first documented progression or death due to any cause, as assessed separately by investigator and central independent reviewer per RANO criteria.

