The study day will be displayed in the data listings. If an event starts before the reference start date, the study day displayed on the listing will be negative.

The reference day for all calculations for the analysis of crossover subjects will be first date when a non-zero dose of either dabrafenib or trametinib was administered.

Time unit

A year length is defined as 365.25 days. A month length is 30.4375 days (365.25/12). If duration is reported in months, duration in days will be divided by 30.4375. If duration is reported in years, duration in days will be divided by 365.25.

Baseline

For efficacy evaluations, the last non-missing assessment, including unscheduled assessments on or before the date of randomization is taken as the "baseline" value or "baseline" assessment. In the context of baseline definition, the efficacy evaluations also include PRO.

For safety evaluations, the last available assessment on or before the date of start of study treatment is defined as the "baseline" assessment. In the rare case that time of assessment and time of treatment start is captured, the last available assessment before the treatment start date/time is used for baseline. If there is more than one record on the same day of screening the highest value would be considered as baseline. For laboratory data, if there is more than one record on the same day of screening, then records from central laboratory should take precedence over local laboratory records.

If patients have no value as defined above, the baseline result will be missing.

On-treatment assessment/event and observation periods

For safety reporting the overall observation period will be divided into three mutually exclusive segments:

- 1. *pre-treatment period*: from day of patient's informed consent to the day before first administration of study treatment
- on-treatment period: from date of first administration of study treatment to 30 days after date of last actual administration of any study treatment (including start and stop date). For crossover patients who start crossover therapy prior to last dose + 30 days, the ontreatment period will end on the day before the first dose of crossover treatment.
- 3. *post-treatment period*: starting at day 30+1 after last administration of study treatment.

Notes: if data on clock time is available in the clinical database (e.g. for time of blood/urine sample taken, ECG performed, etc. and first study treatment administration), a more precise

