Duration of exposure to vincristine overall (days) = (last date of exposure to vincristine as defined in Table 2-7) – (date of first administration of vincristine) + 1.

Induction phase:

Carboplatin is dosed as weekly IV infusions on weeks 1 to 4, and on weeks 7 to 10 followed by 2 weeks of rest in the *induction phase*. Vincristine is dosed as weekly IV bolus infusion for 10 weeks followed by 2 weeks of rest in the *induction phase*. The induction phase refers to the first 12 weeks of dosing (i.e from day of first dose of carboplatin or vincristine until 84 days).

The *last date of exposur* to carboplatin or vincristine in the induction phase is calculated including the rest periods (2 weeks). If subjects continued on to maintenance therapy, the last date of exposure in induction phase is the day before the start of maintenance therapy. If the subject does not continue on to maintenance therapy, the last date of exposure is calculated using the planned cycle duration, i.e. the last date of exposure is the date of first administration (of carboplatin or vincristine) in induction + 83 days. If the subject dies or if the data cutoff date is prior to the calculated date of last exposure, the date will be capped at the date of death or data cutoff.

Maintenance phase:

Maintenance phase will continue for up to a total of 8 cycles, each cycle will be 6 weeks in duration and consists of 4 weekly doses of carboplatin followed by 2 weeks of rest, and three weekly doses of vincristine given concomitantly with the first 3 weeks of carboplatin , followed by three weeks of rest. The maintenance phase refers to the dosing after the first 12 weeks, and will be identified by having at least 9 non-zero doses of Carboplatin, or at least 11 non-zero doses of Vincristine. For Carboplatin/Vincristine, maintenance cycle week1 dates are defined by the following non-zero doses: dose 9/dose 11, dose 13/dose 14, dose 17/dose 17, dose 21/dose 20, dose 25/dose 23, dose 29/dose 26, dose 33/dose 29, and dose 37/dose 32, respectively.

The *last date of exposur* to carboplatin or vincristine in the induction phase is calculated including the rest periods (2 or 3 weeks). The last date of exposure is calculated using the planned cycle duration, i.e. the last date of exposure is the date of last week 1 administration (of carboplatin or vincristine) in maintenance +41 days. If the subject dies or if the data cutoff

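### LGG final SAP: crude by-arm AE percentages do not allow for unequal time at risk between a fixed chemotherapy course and open-ended dabrafenib plus trametinib

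*SAP*

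**What the plan says.** All references are to the final LGG SAP unless stated otherwise.

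- **Objective (1.2).** Safety is a between-arm objective: "Evaluate the safety and tolerability of dabrafenib in combination with trametinib versus carboplatin with vincristine".
- **Measure (2.8.1).** "AEs will be summarized by number and percentage of patients having at least one AE", and likewise for each SOC and PT. "The following AE summaries will be produced by treatment group", covering all and related AEs, SAEs, fatal AEs, and AEs leading to discontinuation or dose change. AESIs (2.8.1.1) are also given as number and percentage of patients, by arm.
- **Window (2.1.1).** Only on-treatment events count, that is "from date of first administration of study treatment to 30 days after date of last actual administration of any study treatment". For control patients who cross over within those 30 days, the window closes the day before the first crossover dose.
- **Control course (1.1 and 2.4.1).** Induction takes 10 weeks plus 2 weeks of rest. "Maintenance phase will continue for up to a total of 8 cycles, each cycle will be 6 weeks in duration".
- **D+T course (1.1).** "Patients on dabrafenib and trametinib therapy may continue to receive the assigned study treatment until disease progression by RANO criteria" or loss of clinical benefit, among other reasons to stop. Treatment beyond progression is possible: "Patients receiving dabrafenib with trametinib who have disease progression by RANO criteria may continue study treatment", subject to conditions.
- **Allowance for time at risk.** Kaplan-Meier time to first occurrence is defined in 2.8.4.11, with censoring no later than the end of the on-treatment period. Section 2.8.1.1 invokes it for AESIs only, if there are enough events. Duration of exposure is tabulated by arm (2.4.1) but does not enter the AE tables.

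**The concern.** A crude percentage of patients with at least one event depends on how long patients are watched as well as on the event rate. One arm has a fixed number of cycles and the other has no planned end, and the counting window follows treatment in each. If D+T patients stay on treatment longer than the chemotherapy course, they have more time to record a first event, and the D+T column can be higher with no difference in rate. The number-of-occurrences table for SAEs has the same weakness, because counts also grow with exposure.

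At stake is the reading of the randomised safety comparison. The primary response analysis is not affected. The tables left without any time adjustment are the general ones: overview, SOC and PT, SAEs, and AEs leading to discontinuation. The AESIs that may receive a time-to-event analysis are defined around D+T toxicity, not chemotherapy toxicity.

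**Working it through.** **1. Length of the control course.**
- Inputs: induction 10 + 2 = 12 weeks (1.1); maintenance 8 × 6 = 48 weeks (2.4.1). Total 12 + 48 = 60 weeks. The SAP does not print this total.
- Check against the SAP's own example (2.4.1, Table 2-7), which places carboplatin dose 29 and vincristine dose 26 at week 43. Maintenance cycle 6 starts at week 12 + 5 × 6 + 1 = 43. The carboplatin dose number is 8 + 5 × 4 + 1 = 29, and the vincristine dose number is 10 + 5 × 3 + 1 = 26. All three agree, so the calendar is reproduced.
- On schedule, the last carboplatin dose falls on day (12 + 7 × 6 + 3) × 7 + 1 = 400. The window then closes on day 430, or 430/7 = 61.4 weeks.
- The 60 weeks is nominal. In the carboplatin example (2.4.1, Table 2-10), induction lasts 90 days against a planned 84, and two maintenance cycles last 86 days against a planned 84.

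**2. Size of the distortion (illustration).** Assume the same constant hazard in both arms and 20% of control patients with a given AE over 60 weeks. Over t weeks the expected crude percentage is 1 − (1 − 0.20)^(t/60).

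| Weeks on treatment, all patients (assumed) | Crude incidence |
|---|---|
| 60 | 20% |
| 104 | 1 − 0.8^1.733 = 32% |
| 156 | 1 − 0.8^2.6 = 44% |

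Adding the 30-day tail to both arms (control 61.4 weeks; D+T 108.3 and 160.3 weeks) gives 32.5% and 44.1%, so the tail hardly matters.

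**3. When the effect is small or reverses.** Using the 61.4-week control window:
- Rare event: 5% in control becomes 8.6% at 108.3 weeks, an excess of 3.6 points.
- Near-universal event: 90% becomes 98.3%, an excess of 8.3 points.
- Shorter D+T observation: with 52 weeks observed, a 20% control figure corresponds to 17.2%, and the bias runs the other way.
- Events confined to the first weeks of treatment: later exposure adds nothing.

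**4. What the alternatives would show.** In the step 2 example the hazard is −ln(0.8)/60 = 0.00372 per week. Times 365.25/7 = 52.18 weeks per year, this is 0.194 per year, or 19.4 patients with a first event per 100 patient-years at risk in both arms. Cumulative incidence at 60 weeks, with censoring, is 20% in both arms. Either measure shows equality where the crude percentages do not.

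**The case against.** The strongest defence is that the tables are descriptive. No AE test, risk difference or interval is planned, and 2.7.2 says no inferential analysis will be done for any secondary objective. Exposure is tabulated by arm, so a reader can see an imbalance. On-treatment incidence is also a fair description of each strategy as given. This stands as far as it goes: nothing in 2.8.1 is stated wrongly, and the crude tables should stay. It does not remove the distortion once the two columns are read against each other, which the objective invites.

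Stronger readings are tempting but not supported:

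- **That longer follow-up will make D+T look more toxic.** The SAP gives no actual D+T exposure. The effect fades for early or near-universal events and reverses if D+T exposure is short, and true differences in rate may outweigh it.
- **That the final cut-off guarantees about 104 weeks at risk.** The two-year minimum (1.1 and 2.1) is survival follow-up. A D+T patient who stops at week 30 contributes about 34 weeks to the AE window.
- **That chemotherapy is capped at 60 calendar weeks.** The SAP caps cycles, and its own example shows delays. A footnote to the PRO windows in LGG SAP Amendment 1 (Table 2-4) mentions about 60 months. That document is superseded for the final analysis, and the current schedule yields 60 weeks.
- **That no time-adjusted method exists.** The Kaplan-Meier analysis in 2.8.4.11 handles unequal time at risk, and it is a partial mitigation for AESIs when it is triggered.

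**Conclusion.** The concern holds in moderate form. The final LGG SAP fixes crude on-treatment percentages as the by-arm measure for AEs, SAEs and AESIs, while time at risk is bounded by design in one arm and open-ended in the other. For events that keep accruing, this may inflate the apparent D+T incidence. In the illustration the excess is about 12 points at 104 weeks (32% against 20%) and 24 points at 156 weeks (44% against 20%). This rests on equal constant hazards, a completed control course, and D+T durations that are assumed and applied to every patient. It shows the mechanism and does not predict the bias in this trial. Crude percentages alone cannot tell the reader which case applies, and for the general AE tables the SAP plans nothing that can. This is a worthwhile, inexpensive improvement to a stated secondary comparison.

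**What to change.** Keep the crude tables. For the key LGG categories (any AE, grade 3 or higher, SAE, AE leading to discontinuation, each AESI and the most frequent PTs), add to 2.8.1 and 2.8.1.1, by arm:

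1. **Exposure-adjusted incidence:** patients with a first event per 100 patient-years at risk, with 95% CI. Time at risk runs from first dose to the first event or, without one, to the end of the on-treatment period.
2. **Cumulative incidence at a common time of about 60 weeks,** with censoring at the end of the on-treatment period. This extends the method in 2.8.4.11, with death as a competing event if needed, and should not depend on a judgement that events are sufficient.

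Base between-arm safety statements on these two measures.

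A crude table truncated at 60 weeks plus 30 days would not do instead. Patients who stop early, or control patients who cross over, leave the on-treatment period before that time, so time at risk would still differ.

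The cost is a few extra tables from data already collected. The exposure-adjusted rate assumes a roughly constant hazard; the common-time cumulative incidence does not, and covers that weakness.
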